## **OUTCOMES AND COVARIATES**

### Primary Pharmacodynamic Endpoint

- Decrease in combined CD4, CD8, and monocyte proportions in BAL fluid

### Secondary Pharmacodynamic Outcomes

- Change in the individual proportions of immune cell in BAL fluid:
  - Tregs
  - CD4 T

- CD8 T
- B cells
- NK cells
- Macrophages
- Monocytes
- Neutrophils

#### Efficacy Endpoints

- All-cause mortality at Day 60
- Number of days on mechanical ventilation after randomization
- Number of Days in the Hospital after randomization
- Number of Days in the ICU after randomization

#### Safety Endpoints

- Pre-defined changes in cardiac conduction
- The incidence of TEAEs and SAEs
- The intensity and relationship of TEAEs and SAEs
- Changes in serial SOFA scores
- Mortality at Day 30

#### Baseline Patient Characteristics

Patient demographic and baseline characteristics will be summarized by mean, standard deviation, median, minimum, and maximum for continuous variables; and by counts and percentages for categorical variables. There will be no formal hypothesis testing for comparison of baseline characteristics between treatment arms.

## **STATISTICAL CONSIDERATIONS**

#### Methods to assess assumptions

Histograms and boxplots will be used to graphically assess normality of the outcomes. Residual diagnostics will be examined and relevant assumptions will be assessed using graphical display and statistical testing where appropriate. In situations where modeling assumptions are in question, nonparametric methods, transformations, or inclusion of higher order terms, may be applied.

#### Missing data

Every effort will be made to minimize missing data. Field validations will be programmed into the REDCap project, with fields marked as 'required' as appropriate, to prevent missing data. Data quality rules within REDCap will allow for checks for missing data, and data status and quality reports throughout the duration of the trial will be reviewed on an ongoing basis. If missing values are identified, the DCC will contact the site study coordinator to resolve all issues. The REDCap Data Resolution Workflow will be used to monitor resolution of all data queries and the project coordinator will confirm responsiveness by the study teams. Before performing any final analyses, the database will be assessed for any remaining missing data. Frequency and reasons for missing data will be reported, as available.

## **STATISTICAL ANALYSES**

#### Pharmacodynamic Analysis

Primary analyses will leverage descriptive statistics to summarize the change in combined proportions of CD4, CD8, and monocytes in BAL fluid by dose arm. Point estimates and corresponding 95% confidence intervals will be reported. We will explore ANCOVA models to compare the difference in post-dose proportions by arm, adjusting for pre-dose levels. Normality assumptions will be assessed and in the event of violation of assumptions, transformations or nonparametric approaches will be considered. Subsequent pairwise comparisons of each dose arm to placebo arm will be assessed as appropriate. Similar methods will be employed for additional flow cytometry endpoints as described above.

Exploratory analyses may also consider unsupervised methods including hierarchical clustering to further identify and visualize patterns in flow cytometry data.

Following single-cell RNA-sequencing, variable genes will be identified using a likelihood-ratio test in DESeq2. K-means clustering will then be used with selected genes to identify homogenous clusters with unique gene expression.

#### Efficacy Analysis

The date of each hospital admission and discharge will be collected for each subject. The number of days in the hospital after randomization will be summarized by treatment group. We will explore nonparametric comparisons of days in hospital after randomization between arms. Similar analyses will be employed for number of days on mechanical ventilation after randomization and number of days in the ICU after randomization.

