Sample Size Calculation:	Sample size considerations were based on precision estimates and the ability to construct 95% confidence intervals around point estimates for pharmacodynamics endpoints with reasonable precision. Sample sizes as small as 9 patients per arm will allow for construction of 95% confidence intervals with half-widths as small as 0.77 standard deviation units. For other assessments, the study is not powered for analysis with inferential statistics. All data will be summarized using descriptive statistics only. Continuous data will be summarized with number of patients (n), mean, median, minimum, maximum, standard of deviation, coefficient of variation and or geometric mean. Categorical data will be summarized with number and proportion of patients.

Table of Contents

Sponsor Approval and Signature Page	2
Synopsis	3
List of Tables	14
List of Terms and Abbreviations	15
1 INTRODUCTION	17
1.1 COVID-19.....	17
1.2 Overview of CM4620	18
1.3 Pre-Clinical Development of CM4620	18
1.3.1 Pre-Clinical Safety and Toxicology Studies.....	18
1.3.2 Preclinical Efficacy Studies	19
1.4 Clinical Development of Auxora	19
1.4.1 Single Ascending Dose and Multiple Ascending Dose Studies	19
1.4.2 Open Label Study in Patients with Acute Pancreatitis with Accompanying SIRS and Hypoxemia (CM4620-201)	22
1.5 Pharmacodynamic and Pharmacokinetic Study in Patients with Acute Pancreatitis (CM4620-202)	24
1.6 Study in Severe Covid-19 Pneumonia (CM4620-204).....	24
1.7 Rationale for Current Study and Selected Doses	25
2 OBJECTIVES AND ENDPOINTS.....	26
2.1 Primary Objective	26
2.2 Secondary Objectives.....	26
2.3 Endpoints	26
3 INVESTIGATIONAL PLAN	27
3.1 Study Design.....	27
3.2 End of Study	28
3.3 Sponsor Termination of the Study	28
4 SELECTION OF PATIENTS	29
4.1 Inclusion Criteria	29
4.2 Exclusion Criteria	29
4.3 Re-Screening.....	30
5 TREATMENT OF PATIENTS	31
5.1 Overview.....	31
5.2 Discharge Criteria	31
5.3 Prohibited Medications	32

5.4	Compliance	32
6	PROCEDURES	33
6.1	Enrollment Procedures.....	33
6.2	Discontinuation and Withdrawal	33
7	STUDY DRUG MATERIALS AND MANAGEMENT	34
7.1	Auxora Product Description	34
7.2	Placebo Product Description.....	34
7.3	Auxora and Placebo Storage.....	34
7.4	Auxora and Placebo Preparation.....	34
7.5	Auxora and Placebo Administration.....	35
7.6	Packaging and Labeling.....	35
7.7	Accountability, Handling and Disposal	36
8	VISITS AND STUDY SPECIFIC ASSESSMENTS.....	37
8.1	Screening.....	37
8.2	Baseline Assessment.....	37

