4.2 Exclusion Criteria

Patients with any of the following conditions or characteristics must be excluded from randomizing:

1. Expected survival or time to withdrawal of life-sustaining treatments expected to be <7 days;
2. ECMO;
3. Invasive mechanical ventilation for more than 7 days
4. Suspected septic shock;
5. The patient has a history of:
 - a. Organ or hematologic transplant;
 - b. HIV;
 - c. Active hepatitis B, or hepatitis C infection;

6. Current treatment with:
 - a. Chemotherapy;
 - b. Immunosuppressive medications or immunotherapy (see [Section 5.3](#) for list of prohibited immunosuppressive medications and immunotherapy) at the time of consent;
 - c. Hemodialysis or Peritoneal Dialysis;
7. The patient is known to be pregnant or is nursing;
8. Currently participating in another study of an investigational drug or therapeutic medical device at the time of consent;
9. Allergy to eggs or any of the excipients in Auxora.

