10.6.2 Number of Days in the Hospital

The date of each hospital admission and discharge will be collected for each subject. The number of days when subjects are still alive and out of hospital during the first 30 Days of the study will be summarized by treatment group. We will explore nonparametric comparisons of days in hospital after randomization between arms.

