10.6.3 Number of Days in the ICU and Days on Mechanical Ventilation

The analysis will be the same as the number of days in the hospital

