### Power Considerations

Sample size considerations were based on precision estimates and the ability to construct 95% confidence intervals around point estimates for pharmacodynamics endpoints with reasonable precision. Sample sizes as small as 9 patients per arm will allow for construction of 95% confidence intervals with half-widths as small as 0.77 standard deviation units.

For other assessments, the study is not powered for analysis with inferential statistics.

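### Days in hospital, in ICU and on the ventilator are compared as raw counts with no score for death and no time window, and SAP and protocol differ on the summary measure

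*SAP*

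**What the plan says.** SAP, Efficacy Analysis: "The number of days in the hospital after randomization will be summarized by treatment group". Nonparametric comparisons of the same quantity between arms are to be explored, and "Similar analyses will be employed for number of days on mechanical ventilation after randomization and number of days in the ICU after randomization". Neither this section, nor the endpoint list, nor the Missing data section says how a patient who dies is scored or when counting ends.

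Protocol 10.6.2 has a different summary: "The number of days when subjects are still alive and out of hospital during the first 30 Days of the study will be summarized". Its next sentence returns to raw days: "We will explore nonparametric comparisons of days in hospital after randomization between arms". Section 10.6.3 carries the approach over to ICU and ventilator days: "The analysis will be the same as the number of days in the hospital". The endpoint names in Protocol 2.3 and 10.2 are raw days as well.

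So the documents differ on the summary measure and share the raw-day comparison.

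The efficacy analysis follows intention to treat and keeps every randomized patient (Protocol 10.3.1; SAP, Analysis population). That includes patients who die or are extubated early and are replaced under Protocol 6.1.

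**The concern.** All patients are ventilated at entry, and Protocol 1.1 cites 49% case fatality in critical disease, adding that mortality may be falling. Death is therefore a common way for a day count to end. The plain reading of raw days is that counting stops at death, which makes an early death look like a short stay. An arm that keeps more patients alive can then show more hospital days, and the descriptive means and medians are affected as much as the comparison.

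The open time window also has a data side. Protocol 8.11 lists recording of extubation up to Day 30, and the Day 60 contact in 8.12 does not list it, so ventilator days beyond Day 30 have no listed source.

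**Working it through.** **The plan's own figure.** No precision figure is given for these endpoints. The only one, a half-width of 0.77 SD with 9 patients per arm, reproduces as t(0.975, 8 df)/√9 = 2.306/3 = 0.769. It does not bear on this point.

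**Same score, opposite outcomes.** Death on day 14 and extubation on day 14 both give 14 raw ventilator days. Days alive and off the ventilator to Day 30 are 0 and 30 − 14 = 16 (no re-intubation).

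**Inputs for hospital days.**
- Placebo mortality p0 = 0.49 (Protocol 1.1); Auxora p1 = 0.30 (assumed).
- Death at D = 13.5 days, the midpoint of the 10 to 17 days in Protocol 1.6. Those deaths were in patients not ventilated at entry, so this is a rough stand-in.
- Survivor stay L = 20 to 28 days, equal in both arms (assumed).

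**Fixed times.** Mean raw days per arm are p·D + (1 − p)·L, so Auxora minus placebo is (p0 − p1)(L − D). Mean days alive and out to Day 30 are (1 − p)(30 − L), so the difference is (p0 − p1)(30 − L).

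| L | Raw days, Auxora minus placebo | Alive and out, Auxora minus placebo |
|---|---|---|
| 20 | 0.19 × 6.5 = +1.24 | 0.19 × 10 = +1.90 |
| 25 | 0.19 × 11.5 = +2.19 | 0.19 × 5 = +0.95 |
| 28 | 0.19 × 14.5 = +2.76 | 0.19 × 2 = +0.38 |

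The arm with fewer deaths has the longer raw stay and more days alive and out. For L = 25 the reversal ends once Auxora survivors leave at (0.49 × 13.5 + 0.51 × 25 − 0.30 × 13.5)/0.70 = 15.315/0.70 = 21.88 days, about 3.1 days sooner.

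**Simulation.** There were 40,000 trials in the base case, with gamma-distributed times (coefficient of variation 0.5, assumed) and all Auxora pooled against all placebo. Arms are 12:4 (protocol cohorts 4 + 4 + 8 at 3:1) or 15:5 (SAP cohorts 4 + 8 + 8). The first figure is the mean probability that an Auxora patient ranks better than a placebo patient. The percentage is the share of trials where that probability falls below 0.5. Unless stated, mean death day is 13.5, stay is 25 days and arms are 12:4.

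- 49% vs 30%: raw 0.444 (60.6%); alive and out 0.566 (30.3%). At 15:5: raw 0.445 (64.4%); alive and out 0.567 (29.6%).
- 35% vs 20% (assumed): raw 0.456 (58.1%); alive and out 0.553 (34.5%).
- 49% vs 49%, same timing: raw 0.500 (47.6% each way, 4.8% ties).
- 49% vs 49%, mean death day 17 vs 10: raw 0.388 for the arm that dies later; alive and out 0.499.
- 30% vs 25% (assumed): raw 0.485 (51%).
- 49% vs 30%, mean death day 20: raw 0.476 (53%).
- 49% vs 30%, 15-day stay: raw 0.489 (50%).
- 49% vs 30%, no deaths before day 7: raw 0.450 (59.2%); alive and out 0.566 (29.8%).
- 49% vs 30%, Auxora survivors leaving at 20 vs 25 days: raw 0.517 (43.8%); alive and out 0.632 (17.1%).

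**Ventilator days**, 49% vs 30%, survivor durations of 10, 14 and 20 days: raw 0.530, 0.496, 0.461; alive and off the ventilator 0.594, 0.593, 0.581. ICU days were not computed.

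**The case against.** **The endpoints carry little weight.** The SAP says so: "For other assessments, the study is not powered for analysis with inferential statistics". The protocol synopsis adds: "All data will be summarized using descriptive statistics only". The rationale in Protocol 1.7 bases dose selection on BAL markers, and escalation follows safety events. This stands and limits the impact. It does not remove the problem, because the fault lies in the quantity measured and affects the descriptive summary too.

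**Deaths are visible elsewhere.** Kaplan-Meier mortality is planned (SAP, Safety Analysis; Protocol 10.6.1). That lets a reader see the deaths but does not correct the day counts.

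**Early deaths are screened out.** Exclusion 1 covers "Expected survival or time to withdrawal of life-sustaining treatments expected to be <7 days". Taken to its limit, it hardly changes the result (0.450 against 0.444).

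**The size depends on assumptions.** This stands. Mortality gaps, stays and death times are assumed or borrowed, replacement patients are not modelled, and with a small mortality gap, later deaths or a 15-day stay raw days sit close to the no-difference case.

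**The remedy has a price.** This also stands. In the base case about 51% of Auxora and 64% of placebo patients score zero; at a 35-day stay, about 69% and 77%. With equal 30% mortality and stays of 20 vs 25 days, raw days do no worse (0.58 against 0.57).

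**Stronger readings.** A reader might infer that the SAP has overridden the protocol, or that comparing raw days is the SAP's own departure. The SAP does not say that it supersedes Protocol 10.6.2 and 10.6.3, and the raw-day comparison is in both documents. A reader might also infer that the planned analysis will reverse a benefit. The documents leave the scoring of deaths open; reversal needs the stop-at-death reading and a sizeable mortality or timing difference.

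**Conclusion.** The point holds as a gap in specification and a mismatch between the documents. On the plain reading that counting stops at death, raw days mix survival with recovery when mortality or timing of death differs between arms. For hospital days, in the assumed 49% vs 30% case, about 60% of trials point the wrong way, some 13 points above the 47.6% seen with no difference; days alive and out give about 30%. The effect is small for a 5-point mortality gap and absent when mortality and timing are equal. For ventilator days it is mainly dilution. The consequence is confined to interpreting exploratory endpoints; the pharmacodynamic endpoint and the sample size are untouched. It should be fixed, because the remedy is cheap and settles the scoring of deaths before outcomes are known.

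**What to change.** Reconcile the SAP's Efficacy Analysis with Protocol 10.6.2 and 10.6.3. For both the summary and the nonparametric comparison, use days alive and out of hospital, alive and out of ICU, and alive and off mechanical ventilation, from randomization through Day 30. Score deaths by Day 30 as 0. Count days after readmission, ICU return or re-intubation as not free. Report raw days only descriptively, beside the number of deaths. Align the endpoint names in Protocol 2.3 and 10.2 and in the SAP endpoint list.

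State the downsides: many zeros when stays are long, no gain when mortality is equal, and a slight change from Protocol 10.6.2 for a patient who dies after discharge.

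The cost is wording plus a CRF check. Hospital admission and discharge dates are already collected. Protocol 8.11 lists extubation only from 168 hours, and the 24 to 144 hour visits do not list it, although Protocol 6.1 foresees extubation before the second BAL, which falls earlier than 168 hours. ICU and re-intubation dates are not listed either. Check the CRF for all three and add fields where absent; raw counts would need them too.

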#### Pharmacokinetic Analysis

Refer to protocol for more details. CalciMedica will be responsible for implementing PK analyses.

#### **TECHNICAL DETAILS**

The SAP will be subject to version control, and we anticipate modifications to analytic plans to be documented herein. As in any study, the analytic plan may change due to assumption violations, logistical issues, unexpected empirical distributions of study outcomes, or a combination thereof. In these cases, the SAP will be

updated accordingly. All analyses will be performed via SAS version 9.4 or higher (The SAS Institute; Cary, NC) or R version 3.6.0 or higher (The R Foundation for Statistical Computing platform). Table and figure formatting and style may be dictated by mode of dissemination or specific target journal(s) for results dissemination.
